12.3 Reporting of Adverse Events

Report initiation for all AEs and serious adverse events (SAEs) will begin immediately after the first infusion of [¹⁸F]F-AraG (Visit 2) and continue until the Day 7 follow up. The Day 7 adverse event assessment may be telephonic and does not require an office visit. All events will be followed to resolution or until they are considered to be not clinically significant according to the investigator's judgment.

All AEs must be recorded in the subject's medical records and on the CRF. AEs will be reported using customary medical terminology along with the following information: the onset and end dates, whether the event is at the site of [¹⁸F]F-AraG administration, whether the event is considered to be a SAE, the impact the event had on study treatment, the CTCAE grade (intensity) of the event, the causality of the event, whether treatment was given as a result of the event, and the outcome of the event.

Serious Adverse Events

An AE should be classified as an SAE if any of the following criteria are met:

- It results in death (i.e., the AE actually causes or leads to death).
- It is life threatening (i.e., the AE, in the view of the investigator, places the subject at immediate risk of death. It does not include an AE that, had it occurred in a more severe form, might have caused death.).
- It requires or prolongs inpatient hospitalization.
- It results in persistent or significant disability/incapacity (i.e., the AE results in substantial disruption of the subject's ability to conduct normal life functions).
- It results in a congenital anomaly/birth defect in a neonate/infant born to a mother exposed to the investigational treatment.
- It is considered a significant medical event by the investigator based on medical judgment (e.g., may jeopardize the subject or may require medical/surgical intervention to prevent one of the outcomes listed above).

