5. STUDY DESIGN

Protocol CST-FARAG-203 is a pilot study using the uEXPLORER total-body PET/CT system to acquire dynamic [¹⁸F]F-AraG scan data in healthy individuals and patients with NSCLC.

Screening will consist of eligibility confirmation, the patient signing the consent form, and any assessments outlined in the study calendars below. This will also include a query about status and date of COVID-19 vaccination.

Eligible healthy subjects will undergo a single dynamic [¹⁸F]F-AraG PET/CT scan (of duration up to 90-minutes) on the uEXPLORER PET/CT scanner within 28 days of screening or on the day of screening if possible and convenient to the subject. There will be a follow-up visit or call 7 days after the scan to assess any AEs that could be attributed to either the scan or the administration of [¹⁸F]F-AraG.

Eligible subjects with NSCLC who are planned to receive PD-1/PD-L1 immunotherapy will undergo a pre-therapy dynamic [¹⁸F]F-AraG PET/CT scan, and an optional post-therapy (first dose only) dynamic [¹⁸F]F-AraG PET/CT scan on the uEXPLORER total-body scanner.

For each enrolled patient, [¹⁸F]F-AraG will be administered by a licensed Nuclear Medicine technologist under the supervision of a board-certified Nuclear Medicine physician (ABNM or ABR certified) on an outpatient basis. It will be administered as a single bolus injection of 5 mCi +/-20% IV into a vein. Vital signs will be assessed just prior to and after completion of dynamic [¹⁸F]F-AraG PET scan.

For each scan, the subject will be prepared according to the site's standard procedures and asked to void the bladder immediately prior to imaging. For the scan, an intravenous (IV) line will be placed in a vein and the subject will be positioned supine on the scanner table. The PET/CT imaging will begin with a low-dose CT scan on the uEXPLORER PET/CT scanner. This CT scan will provide information for anatomic localization and attenuation correction purposes.

[¹⁸F]F-AraG will then be infused as above and a 90-minute dynamic PET scan will be performed on the uEXPLORER. The IV line will be removed after dynamic acquisition. For subjects who may not be able to undergo a 90-minute dynamic scan, a 60-minute dynamic PET scan will be performed, followed by a 10-minute static scan starting at 80 minutes post [¹⁸F]F-AraG infusion. The separate static scan at 80 minutes will be obtained along with an ultra-low-dose CT which is needed for attenuation correction of this separate scan.

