5.1 Study Calendar

Table 1: Study Schedule of Events (Healthy Volunteers)

Protocol Assessments	Visit 1 ¹	Visit 2 ¹	Safety Interview (Day 7)
	Screening (Day -28 to Day 0)	PET/CT scan (Day 0)	
Informed consent	X		
Medical History and Physical Examination ²	X		
Eligibility Assessment	X	X	
Urine Pregnancy Test ³	X	X	
Concomitant medications	X	X	
[¹⁸ F]F-AraG PET/CT imaging		X	
Adverse events collection ⁴		X	X ⁵

1. Visits 1 & 2 can be merged into a single visit done on the same day.
2. Includes vital signs, height, weight, BMI
3. In women of 18-60 years old unless documented hysterectomy or bilateral ovarian removal is available.
4. AE collection: Up to 2 hours of [¹⁸F]F-AraG infusion on Day 0; AEs that occur prior to this will be considered baseline.
5. The follow up safety interview can be performed telephonically and does not require a separate in-person visit.

Table 2: Study Schedule of Events (NSCLC subjects)

Protocol Assessments	Visit 1	Visit 2	Visit 3	Visit 4 ^Ψ	
	Screening (Day -28 to Day 0)	PET/CT scan (Day 0)	(Day 0-7)	PET/CT (7-14 Days after V3)	Safety Interview (7 days after last PET/CT scan)
Informed consent	X				
Medical history and Physical Examination ²	X				
Eligibility Assessment (including eligible lesions assessment)	X	X			
ECOG Performance Status Assessment	X				
SOC CT/MRI and/or FDG-PET/CT collection	X ¹				
Urine Pregnancy Test ³	X	X		X	
[¹⁸ F]F-AraG PET/CT imaging		X		X	
Administration of PD-1/PD-L1 Treatment			X		
Adverse events collection ⁴		X		X	X ⁵
Concomitant medications	X	X		X	

1. CT or MRI or FDG-PET/CT performed up to 45 days prior to Visit 2 is acceptable.

2. Includes vital signs, height, weight, BMI

3. In women 18-60 years old unless documented hysterectomy or bilateral ovarian removal is available

4. AE collection: Up to 2 hours of [¹⁸F]F-AraG infusion on Visits 2 and 4; AEs that occur prior to this will be considered baseline.

5. The follow up safety interview can be performed telephonically and does not require a separate in-person visit.

^Ψ Optional visit

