7. RISKS TO SUBJECTS

7.1.1 Risks from [¹⁸F]F-ArA/G PET/CT scan

In this study, 2-4 healthy subjects and 2-4 NSCLC patients will undergo research PET/CT imaging with [¹⁸F]F-ArA/G as specified in the experimental imaging section. [¹⁸F]F-ArA/G PET imaging has been performed on 6 healthy volunteers in a separate study with no drug-related side effects. In addition, [¹⁸F]F-ArA/G has been administered to 13 cancer patients with 7 of those patients getting two doses for pre and post immunotherapy scans, also without any drug-related side effects.

Given the prior clinical safety experience thus far, we expect few, if any, adverse effects from [¹⁸F]F-ArA/G administration in this study. Presently there are no standard surrogate biomarkers or imaging modalities that can substitute for these procedures. The alternative will be for the patient to withdraw from the imaging study.

The safety monitoring practices employed by this protocol are adequate to protect the subjects' safety and should detect all Treatment Emergent Adverse Events (TEAEs). An indirect health benefit to the subjects enrolled in this trial is the free medical tests received at screening and during the study.

Due to the (up to) 90-minute long scan time through which the participants are expected to remain still, the patients may feel discomfort and/or fatigue from laying on the scanner table. In addition, they may experience claustrophobia from being inside the scanner bore, which is a partially enclosed space.

Another risk is possible bruising and/or infection at the IV site.

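### AE/SAE recording opens after the tracer infusion, so procedure harms that begin earlier, at IV-line placement, positioning or CT, are labelled baseline

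*Combined protocol and SAP*

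**What the plan says.** **When recording starts.** Section 12.3: "Report initiation for all AEs and serious adverse events (SAEs) will begin immediately after the first infusion of" the tracer at Visit 2. Reporting then runs to the Day 7 follow-up.

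**What happens to earlier events.** Footnote 4 of Table 1 (healthy volunteers): "AEs that occur prior to this will be considered baseline". Footnote 4 of Table 2 (NSCLC) applies the same rule to both scan visits: "Visits 2 and 4; AEs that occur prior to this will be considered baseline".

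**What comes before the tracer.** Section 5 gives the scan-day order. First, "an intravenous (IV) line will be placed in a vein and the subject will be positioned supine on the scanner table". Next, "The PET/CT imaging will begin with a low-dose CT scan on the uEXPLORER PET/CT scanner". Only after that is the tracer given: it "will then be infused as above and a 90-minute dynamic PET scan will be performed on the uEXPLORER".

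**Which procedure harms are expected.** Section 7.1.1 warns that subjects may feel discomfort or fatigue during the long scan and that "they may experience claustrophobia from being inside the scanner bore". It adds: "Another risk is possible bruising and/or infection at the IV site".

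**Text that points to wider capture.** Section 12.4 makes the investigator responsible for every AE and SAE seen or reported in the course of the study, with no reference to the infusion. For healthy subjects, Section 5 says that the 7-day contact looks for events attributable to the scan as well as to the tracer.

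**The concern.** The study intervention is more than the tracer. It also includes venous access, lying in a long-bore scanner and a CT. Some of this always happens before the reporting window opens, and the footnote then files what happened there with the subject's pre-existing state. Baseline normally means a condition the subject brought to the study, not one that a study procedure has just caused.

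At stake is how completely the safety section describes procedure harms. Section 10.5 lists three safety outcomes: treatment-emergent AEs, withdrawals due to AEs, and SAEs. Only the first is defined by onset on or after the first treatment. The other two have no onset limit in Section 10.5, but the window in Section 12.3 and the label in footnote 4 can keep pre-infusion events out of them. Two sites or monitors could also read the sections differently and record the same event in different ways.

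**Working it through.** The plan gives no figure to reproduce. The check sets the sections side by side and counts the scans affected.

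**1. Scan-day order against the recording rule**

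| Step (Section 5) | Section 12.3, first scan | Footnote 4, any scan |
|---|---|---|
| IV line, supine positioning | window not open | baseline |
| Low-dose CT | window not open | baseline |
| Infusion and dynamic PET | window opens | collected |

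This takes the footnote's reference point to be the infusion, which is its natural reading.

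**2. Which harms named in Section 7.1.1 can start before the tracer**

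- IV site: an immediate injury can. Infection and later bruising would usually appear after the infusion, and the line stays in until the dynamic acquisition ends.
- Claustrophobia: it can, at positioning or CT. Section 5 mentions only the scanner table at this stage. That the subject is in the bore before the tracer is inferred from the CT.
- Discomfort and fatigue: these are tied to the scan of up to 90 minutes, so mostly after the infusion.

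Section 12.2 counts the worsening of an existing condition as an AE. What is left is an early event that does not worsen after the tracer.

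**3. How many scans have an affected interval**

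Inputs: 2 to 4 healthy subjects with one scan each, and 2 to 4 NSCLC subjects with one scan plus an optional second (Sections 2 and 5).

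- First scans: 2 + 2 = 4 at minimum, 4 + 4 = 8 at maximum.
- All scans: 2 + 2 = 4 with no optional scan, up to (4 × 1) + (4 × 2) = 12.

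Under Section 12.3 alone the affected scans are the 4 to 8 first scans. The window opens at the first infusion, and Table 2 puts the safety interview 7 days after the last scan, so the window is already open when a patient arrives for Visit 4. Under footnote 4 the baseline label applies again at Visit 4, giving 4 to 12 scans. An event between IV placement and the second infusion is thus reportable under Section 12.3 and baseline under footnote 4.

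**4. Which outcomes in Section 10.5 are touched**

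- TEAEs: a pre-infusion event at the first scan is outside the definition whatever Section 12.3 says. At Visit 4 its onset follows the first treatment, so the definition already includes it, and footnote 4 is out of line with Section 10.5 as well as with 12.3. Either way, the TEAE definition is not what needs changing.
- SAEs and withdrawals due to AEs: no onset limit in Section 10.5, so a late-opening window can lose events here.

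**5. Subjects who stop before the tracer**

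A consented subject who stops at IV placement or CT on the first scan day receives no infusion. Appendix 2 (items G and H) makes that subject a screen failure, to be replaced, with only the subject number, demographics and reason kept. Section 11.4.3 limits the Safety population to dosed subjects. The harm that ended participation would appear neither in the AE tables nor among withdrawals due to AEs.

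**The case against.** The best defence is that opening AE reporting at first tracer exposure is a coherent convention. It matches the TEAE definition and the Safety population, the study is an exploratory imaging pilot in 4 to 8 subjects, and safety is not among the objectives in Section 3. No time-activity curve or scan-time recommendation is affected. All of that stands, and it limits the weight of the point.

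Three stronger readings are tempting, and the documents do not support them.

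- A reader might infer that pre-infusion harms are never counted. Footnote 4 relabels such events; it does not say to discard them. Sections 12.4 and 12.5 ask for AEs found by any means, Section 12.2 brings back any that worsen, and Section 11.3 puts all collected data in listings. The defect is conflicting instructions and a wrong label, not certain loss.
- A reader might divide one event by the number of subjects and call the result a shift in AE incidence. The incidence outcome in Section 10.5 is treatment-emergent AEs, which the proposed change leaves as defined. The plan also gives no event rate to support such a figure.
- A reader might take all 12 possible scans as affected by Section 12.3. That count needs footnote 4.

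The defence does not answer the contradiction itself. The wider duty in Section 12.4 and the scan-related aim in Section 5 do not override footnote 4, and that aim is stated only for healthy subjects.

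**Conclusion.** The point holds in a narrow form. The plan labels as baseline a small class of events that study procedures cause: immediate IV-site injury, and claustrophobia at positioning or CT, when they begin before the tracer and do not worsen after it. Procedure-related AEs, SAEs and withdrawals due to AEs can be under-reported as a result, on 4 to 8 first scans if Section 12.3 governs and on up to 12 scans if footnote 4 does. TEAE incidence as defined is unaffected.

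This rests on three assumptions: that footnote 4 refers back to the infusion, that the Day 7 follow-up in Section 12.3 is the interview that Table 2 places after the last scan, and that the CT puts the subject in the bore before the tracer. The number of such events cannot be estimated from the documents; it may be small, and the events mostly mild. The change is still worth making, because the sections contradict one another and the correction is cheap.

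**What to change.** 1. Reconcile Section 12.3, footnote 4 of Tables 1 and 2, Section 12.4 and Section 5 so that all give one start for AE/SAE recording: the first study procedure, IV-line placement, on each scan day. This also removes the disagreement at Visit 4.
2. Keep baseline for conditions present before that procedure.
3. Add to Section 10.5 a separate row or listing of procedure AEs with onset before that day's infusion. State that it includes consented subjects who stop before the tracer, although Appendix 2 makes them screen failures and Section 11.4.3 leaves them out of the Safety population.
4. Leave the TEAE definition and the Safety population unchanged.

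Cost: wording in Section 12.3, the two footnotes and Section 10.5, with matching edits in Sections 5 and 12.4 where needed, plus one row or listing. The downside is that a few more minor events will be reported.

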12.4 Methods and Timing for Assessing and Recording Safety Variables

The investigator is responsible for ensuring that all AEs and SAEs that are observed or reported during the study are collected and reported to the FDA in accordance with CFR 312.32 (IND Safety Reports).

12.5 Assessment of Adverse Events

All AEs and SAEs whether volunteered by the subject, discovered by study personnel during questioning, or detected through physical examination, laboratory test, or other means will be reported appropriately. Each reported AE or SAE will be described by its duration (i.e., start and

end dates), regulatory seriousness criteria if applicable, suspected relationship to the investigational treatment (see following guidance), and actions taken.

The guidelines outlined in CTCAE v5.0 will be used for assessing the intensity of the event. The general guidelines for assessing the AE grade appear below. Full guidelines may be obtained at https://ctep.cancer.gov/protocoldevelopment/electronic_applications/docs/CTCAE_v5_Quick_Reference_5x7.pdf

Table 3: CTCAE v5.0 General Guidelines

Grade	Description
Grade 1	Mild; asymptomatic or mild symptoms; clinical or diagnostic observations only; intervention not indicated.
Grade 2	Moderate; minimal, local or noninvasive intervention indicated; limiting age-appropriate instrumental activities of daily living (ADL)*.
Grade 3	Severe or medically significant but not immediately life-threatening; hospitalization or prolongation of hospitalization indicated; disabling; limiting self care ADL†.
Grade 4	Life-threatening consequences; urgent intervention indicated.
Grade 5	Death related to AE.‡

*Instrumental ADL refer to preparing meals, shopping for groceries or clothes, using the telephone, managing money, etc.

†Self care ADL refer to bathing, dressing and undressing, feeding self, using the toilet, taking medications, and not bedridden.

‡Unlike the AE outcome assessment (see Section **Error! Reference source not found.**), a subject may have more than one Grade 5 event.

-Common Terminology Criteria for Adverse Events (CTCAE), v5.0: November 27, 2017

12.6 Causality

Adverse events will be assigned a relationship (causality) to the study treatment. The Investigator will be responsible for determining the relationship between an AE and the study treatment. The type of event, organ system affected, and timing of onset of the event will be factors in assessing the likelihood that an AE is related to the study treatment. Relationship of AEs to study treatment will be classified as follows:

- Not Related: No relationship exists between the AE and the treatment. The event is attributed to a pre-existing medical condition or an intercurrent event unrelated to the study product.
- Possibly Related: Follows the treatment but may have developed as a result of an underlying clinical condition or treatments/interventions unrelated to the study product.
- Probably Related: Follows the treatment but is unlikely to have developed as a result

of the subject's underlying clinical condition or other treatment or other interventions.

- Definitely Related: Follows the treatment and physical evidence shows a convincing relationship to the treatment.

12.7 Reporting Requirements for SAEs

The Investigator is required to report all SAEs. Once the Investigator becomes aware of an SAE, he/she must report the SAE to CellSight within 24 hours at:

[contact]
Email: [contact]

The CellSight Medical Monitor may request additional supporting documentation as it becomes available, such as lab reports, ECG reports, discharge summary, hospital notes, etc.

The Investigator is also responsible for reporting all SAEs to the appropriate Institutional Review Board (IRB) in accordance with local laws and regulations. The Investigator is responsible for maintaining documentation in the study file that indicates the IRB has been properly notified. Under 21 CFR 312.32(c), the sponsor is required to notify FDA and all participating investigators in an IND safety report (i.e., 7- or 15-day expedited report) of potentially serious risks from clinical trials or any other source as soon as possible, but no later than 15 calendar days after the sponsor receives the safety information and determines that the information qualifies for reporting. Participating investigators include all investigators to whom the sponsor is providing drug under any of its INDs or under any investigator's IND (21 CFR 312.32(c)(1)).

13. QUALITY CONTROL AND QUALITY ASSURANCE

13.1 Monitoring Requirements

In an effort to fulfill the obligations outlined in 21 CFR Part 312 and ICH guidelines which require the Sponsor to maintain current personal knowledge of the progress of a study, the Sponsor's designated monitor will visit the center(s) during the study as well as maintain frequent telephone and written communication. The Investigator will permit the Sponsor to monitor the study as frequently as is deemed necessary and provide access to medical records to ensure that data are being recorded adequately, that data are verifiable and that protocol adherence is satisfactory.

The Investigator will permit representatives of the Sponsor and/or designated CRO to inspect all CRFs and corresponding study subject original medical records (source documents) at regular intervals throughout the study. Subject original medical records and other relevant data must be available to support all data recorded in the CRF. In addition to the original medical records, these data may include but are not limited to, study, laboratory and diagnostic reports, wound images and tracings, etc.

Site inspections serve to verify strict adherence to the protocol and the accuracy of the data being entered on the CRFs, in accordance with federal regulations. A Monitoring Log will be maintained at each study site that the monitor will sign, date, and state the type of visit.

The Investigator should be aware that the study site and subject records may be inspected by the Sponsor and or representatives of the designated CRO, FDA, or other regional regulatory authority.

13.2 Acceptability of Case Report Forms

All CRFs will be completed as soon as possible after the subject's visit. Corrections to data on the CRFs will be made according to standard data correction procedures. The Investigator will review CRFs to indicate that, to his/her knowledge, they are complete and accurate. CRFs may be reviewed by the Sponsor's or designated CRO's monitor, who will make a decision as to their acceptability.

13.3 Modification of Protocol

The Investigator will not modify or alter this protocol without first obtaining the concurrence of the Sponsor. Approval by the Investigator's IRB must also be obtained prior to implementation of the change, with two exceptions:

1. When necessary to eliminate apparent immediate hazard to the subject; or
2. When the modification does not involve the subject's participation in the trial.

An amendment may also require modification of the ICF. The Investigator will provide an approval letter for the amendment and revised ICF, if applicable, to the Sponsor. An amendment must be in writing and dated by both the Sponsor and the Investigator. If necessary, the Sponsor will submit protocol amendments to FDA and other appropriate regulatory authorities.

